PROTOCOL TITLE: Coordinated medical treatment of opioid use disorder and infectious disease

Coordinating opioid use treatment through medical management with infection treatment (Project COMMIT)

PRINCIPAL INVESTIGATOR: [name]

NCT04180020

Project COMMIT Study Schedule

| Study Activities | Screening Process | | Study Entry | | Study Participation With Assigned Treatment | | | | | |
|--|-------------------|-----------|----------------------------------|----------------|---|-----|----------------|------|-------|-------|
| | Pre-Screening | Screening | Baseline Randomization/Induction | | Wk 1 | D/C | Wk 4 | Wk 8 | Wk 12 | Wk 24 |
| Intervention (LAB)^d | | | X | | | | X | X | | |
| Blood Buprenorphine Collection^a | | | X ^b | X ^b | | | X ^c | | | |
| Visit Number | | Visit 0 | Visit 1 | | Vis2 | | Vis3 | Vis4 | Vis5 | Vis 6 |
| Eligibility | | | | | | | | | | |
| Contact Primary Team | X | | | | | | | | | |
| Chart Review | X | | | | | | | | | |
| Review Inclusion/Exclusion | X | | | | | | | | | |
| Informed Consent | | X | | | | | | | | |
| Screener | | X | | | | | | | | |
| Laboratory Tests/Diagnostic Procedures | | | | | | | | | | |
| Urine Pregnancy Test | | X | | | | | X | X | X | X |
| Rapid HCV (confirmatory VL if applicable) | | | X | | | | | | X | |
| Rapid HIV (confirmatory test if applicable) | | | X | | | | | | X | |
| Urine Toxicology | | | X | | | | X | X | X | X |
| BMP (SOC) | | | X | | | | | | X | |
| CBC (SOC) | | | X | | | | | | X | |
| INR (SOC) | | | X | | | | | | | |
| LFTs (SOC) | | | X | | | | | | X | |
| HBV Core Ab, Hep B surface Ab, Surface Ag and reflex HBV DNA viral load for positive | | | X | | | | | | | |
| HIV VL (HIV+) | | | X | | | | | | X | |
| CD4+ Count (HIV+) | | | X | | | | | | X | |
| HCV VL (HCV+) | | | X | | | | | | X | |
| Interviews/Questionnaires | | | | | | | | | | |
| Demographics Form | | | X | | | | | | | |
| MINI (SUD, DSM-V d/o) | | | X | | | | | | | |
| AUDIT | | | X | | | | | | | |
| ASRS (for ADHD) | | | X | | | | | | | |
| WHOQOL-Bref | | | X | | | | X | X | X | X |
| PHQ-9 | | | X | | | | X | X | X | X |

| | | | | | | | | | |
|--|--|--|---|---|---|---|---|---|-----|
| PCL5 (PTSD) | | | X | | | | | | X |
| Modified PEG Pain Scale | | | X | | | X | X | X | X |
| Sexual Risk and IDU Risk Behaviors | | | X | | | X | X | X | X |
| Criminal Justice Questionnaire | | | X | | | X | X | X | X |
| Interpersonal Violence | | | X | | | X | X | X | X |
| Timeline Followback | | | X | | | X | X | X | X |
| Covid-19 Questionnaire | | | X | | | X | X | X | X |
| Clinical | | | | | | | | | |
| Medications | | | X | | | X | X | X | X |
| ID Questionnaire | | | X | | | X | X | X | X |
| Substance Use Treatment (SUTx) Form | | | | | | X | X | X | X |
| COWS (as needed including after baseline to start on LAB) | | | | X | X | | X | X | X |
| Elixhauser Comorbidity Index | | | X | | | | | | |
| Safety | | | | | | | | | |
| Modified Systematic Assessment for Treatment Emergent Events (SAFTEE) with sedation/overdose information | | | | | X | | X | X | X |
| Ramsay Sedation Scale | | | X | X | | X | X | X | X |
| Other | | | | | | | | | |
| Implementation Qualitative Interview (study providers, nurse care managers)* | | | | | | | | | X X |

- a. Only for patients randomized to LA-B.
- b. There will be two separate blood buprenorphine sample collections around the first Sublocade® dose. The first collection will be 1 hour prior to initial Sublocade® dose up to 8 hours after. The second collection should occur between 24-48 hours post the initial Sublocade® dose (up to 7 days post-dose).
- c. To occur 28 days (+/- 7 days) post the initial Sublocade® dose. Must be collected prior to the second Sublocade® dose.
- d. Sublocade® injections may be given off study schedule according to provider clinical discretion.

*Interview will be conducted at a time point between week 12 and 24 post-randomization for selected participants.

1.0 Objectives / Specific Aims

This study seeks to test a new model of care (ID/LAB) in which opioid use disorder (OUD) is managed by infectious disease (ID) specialists and hospitalists concurrent with management of the OUD-related infections, using long-acting injectable buprenorphine (LAB), followed by referral as soon as possible after hospital discharge to community resources for long term treatment of OUD.

Specific Aims:

Aim 1: The primary outcome will be a binary indicator of whether a patient is enrolled in and receiving effective medication treatment for OUD (buprenorphine, methadone, or injection naltrexone) at 12 weeks (3 months) after randomization.

Aim 2: Evidence of improved opioid use outcomes (lower days of using opioids, negative urine opioids).

Aim 3: Have higher rates of completion of the antimicrobial regimen for their infectious disease, decreased re-hospitalizations and emergency room presentations related to either their infectious disease or OUD over the 12-week follow-up period, and improved measures of quality of life.

Hypothesis: Assignment to the ID/LAB arm (OUD managed directly by the ID or hospitalist team with long acting injection buprenorphine) will promote greater enrollment in effective medication treatment for OUD at 12 weeks after randomization, compared to TAU.

2.0 Background

The opioid use disorder (OUD) epidemic is a pressing public health crisis. In 2016, more than 64,000 Americans died of drug overdose, surpassing the number of HIV deaths at the peak of the AIDS epidemic.¹ The current OUD epidemic also results in serious infections due to injection drug use (IDU), magnifying morbidity and mortality. Hepatitis C virus (HCV), HIV infections, hospital admissions due to invasive bacterial infections including *Staphylococcus Aureus* bacteremia, endocarditis, skin and soft tissue infections, and bone and joint infections have all increased.²⁻⁴ This population with co-occurring IDU-related infections represents the most severely ill OUD patients, and an important opportunity to intervene, both to improve patients' outcomes, and to reduce the public health risk of infectious disease (ID) transmission.

Currently, treatment of patients with co-occurring OUD and ID is often impeded by inadequately treated OUD. Most hospitals, particularly in under-resourced and rural areas, lack physicians trained in treatment of OUD, and the care offered for these patients typically consists of detoxification and referral to outpatient resources for follow-up treatment. This asks patients with severe OUD to tolerate withdrawal symptoms, risking premature exit from hospital, and relapse to opioid use after failure to connect with OUD treatment referrals. Results include long lengths of stay due to concern about relapse and non-adherence if patients leave the hospital, readmissions after OUD relapse, and lack of antibiotic adherence and reinfection, all leading to both poor clinical outcome and high healthcare costs. Hospital settings that manage these infections are treating increasing numbers of people with untreated OUD. This provides an opportunity to engage patients in treatment of their OUD while managing their infections. Infectious Disease (ID) specialists and hospitalists are a critical and logical resource to build capacity and increase access to medications for opioid use disorder (MOUD). With successful co-treatment of addiction and infectious diseases, OUD could be stabilized, while repeat infections are avoided, and risk of morbidity and mortality due to infection or overdose reduced. Exploring models for co-treatment of infections and OUD thus seems a promising avenue for addressing this complex dimension of the opioid epidemic.

An injectable long-acting formulation of buprenorphine (LAB), which produces therapeutic blood levels for a month, has been recently FDA-approved, and has potential advantages for initiating OUD treatment within hospital settings, including: 1) immediate and sustained treatment of opioid craving and withdrawal symptoms which frequently cause patients to leave against medical advice; 2) involvement of clinicians treating the infections in providing treatment for OUD such that treatment begins early, without waiting for addiction specialist consultation or depending

on referral to treatment after hospitalization; 3) providing a bridge to long term treatment for OUD, reducing opioid relapse and improving completion of antimicrobial treatment. This would seem particularly important for individuals in rural areas where there is limited access to specialty care.

We propose to test a new model of care (ID/LAB) in which opioid use disorder (OUD) is managed by infectious disease (ID) specialists and hospitalists concurrent with management of the OUD-related infections, using long-acting injectable buprenorphine (LAB), followed by referral as soon as possible after hospital discharge to community resources for long term treatment of OUD. Adults admitted to hospital for infections related to OUD (N = 200) will be identified and randomly assigned 1:1 to ID/LAB or treatment as usual (TAU). For this study, TAU will constitute establishment of formal diagnosis for OUD and counseling on recommendation for medication treatment including recommendation to the primary ID/ Medicine team to consider consult for OUD treatment by the typical avenue in each given hospital setting, if available.

The primary outcome measure will be the proportion of patients enrolled in effective medication treatment for OUD (buprenorphine, methadone, or extended-release naltrexone) at 3 months (12 weeks) after randomization. Study sites will be three hospitals serving geographically diverse, mixed urban and rural communities across the Eastern U.S. **The specific aims are to determine whether patients who receive ID/LAB, compared to those receiving TAU will, be more likely at 3 months post-randomization to:**

Aim 1 (primary aim): Be enrolled in medication treatment for OUD at 3 months post randomization.

Aim 2: Evidence of improved opioid use outcomes (lower days of using opioids, negative urine opioids).

Aim 3: Have higher rates of completion of the antimicrobial regimen for their infectious disease, decrease re-hospitalizations and emergency room presentations related to either their infectious disease or OUD over the 12-week follow-up period, and improved measures of quality of life.

3.0 Intervention to be studied

This is a multi-site, randomized controlled trial of adult patients (N = 200) hospitalized with severe bacterial or viral infections (complications of HCV, HIV) related to opioid use disorder (OUD). They will be recruited upon diagnosis of their infection and randomized 1:1 to one of two models of care: 1) Infectious Disease management of OUD with Long-Acting injectable buprenorphine (ID/LAB), vs. 2) Treatment as Usual (TAU). ID/LAB is the new model in which OUD is managed by Infectious Disease (ID) specialists and/or Hospitalists concurrent with management of the infectious diseases, using long-acting injectable buprenorphine (LAB). TAU is designed to systematize what is the current practice at the participating hospitals and in most U.S. hospitals while offering a minimum standard of care. TAU will constitute recommendation for MOUD initiation and consultation for addiction medicine when available; in practice, it is typically detoxification from opioids and referral to community-based addiction treatment after hospital discharge. Both models have as their goal stabilization of the OUD and establishing the patient in effective community-based medication maintenance treatment (buprenorphine maintenance or methadone maintenance) for the long term. The primary outcome measure will be the proportion of patients enrolled in effective medication treatment for OUD (buprenorphine, methadone, or extended-release naltrexone) at 3 months (12 weeks) after randomization. Study sites will be three hospitals serving geographically diverse, mixed urban and rural communities across the Eastern U.S.

Randomization: The randomization scheme will be designed by the study statistician and programmed into the data management system. Participants will be randomized to one of the two study arms (ID/LAB vs TAU) using blocks of 4, stratified by Study Site. As soon as a consenting patient has been determined to be eligible, a member of the study team will enter the data system, register the participant, obtain a unique study ID number, and the randomized group assignment will be generated by the system (ID/LAB or TAU). Treatment under the assigned study arm will then begin.

The FDA approved an injectable monthly formulation of buprenorphine (Sublocade®) on November 30, 2017. Sublocade® is indicated for the treatment of moderate-to-severe opioid use disorder (OUD) and is administered in the subcutaneous tissue of the abdomen. The manufacturer is Indivior, Inc.

Long-acting formulations of buprenorphine represent a potential breakthrough in the treatment of OUDs, reducing the risk of treatment drop-out and clinical relapse. Long-acting formulations of medications in general have been associated with better medication adherence when compared to their oral counterparts⁵⁻⁸. Probuphine®, implantable buprenorphine rods (80 mg per rod, 4 rods are implanted) deliver 6 months of treatment, but at modest blood levels and its FDA approval is for maintenance treatment of patients who are stable on 8mg/day or less of sublingual buprenorphine, not for acute treatment of OUD.⁹ The FDA recently approved an injectable monthly formulation of buprenorphine (Sublocade®) that is administered in the subcutaneous tissue of the abdomen. Two doses are available, 100mg and 300mg. The 300mg dose delivers a far more adequate steady state blood level of 6.54 ng/mL over 28 days, and has been associated with better opioid abstinence outcomes for those who inject heroin¹⁰. Available short-term data support the hypothesis that the injectable would be superior to SL formulation. Data presented to the FDA by Indivior, the manufacturer of Sublocade®, show it is well tolerated and associated with 64-66% retention in treatment at 12 months as compared to only 34% on placebo¹⁰.

For this study, the 300 mg dose will be the starting dose, as it produces blood levels equivalent to the higher dose range of sublingual buprenorphine, and may be more effective among heroin users. For subsequent doses the 100 mg dose can be chosen per clinical judgement (e.g. if significant side effects), although the default will be to continue the 300 mg dose as higher doses/blood levels typically translate into greater clinical efficacy.

Risks of Sublocade® include: increased opioid withdrawal symptoms if the medication is initiated too soon after last opioid dose; opioid related side effects--e.g. nausea, constipation, sedation, respiratory depression (particularly when combined with alcohol or other sedating drugs); side effects related to subcutaneous injection, pain, inflammation, or (rarely) infection at the injection site; worsening of opioid use disorder if the medication does not prove effective or is discontinued by the patient, including functional impairment as well as risk of death from drug overdose.

Treatment As Usual (TAU): There is significant practice variability across the US with regards to inpatient OUD management. For a significant amount of institutions, particularly in rural settings, so called 'detoxification' from opioids with non-opioid agonist medications and referral to outpatient treatment is standard clinical practice. Hence there is a gap between common practice and current best practices, which recommend initiation of MOUD for withdrawal treatment, continued therapy, and transition to the community for long term maintenance. This study will utilize a semi-structured TAU design that ensures a minimum standard of care and also reflects both variations in clinical variability and pragmatic clinical practice. TAU will constitute establishment of formal diagnosis for OUD and counseling on recommendation for medication treatment including recommendation to the primary ID/ Medicine team to consider consult for OUD treatment by the typical avenue in each given hospital setting, if available. Both control and intervention arms will receive opioid overdose education. Note: We considered allowing TAU to remain unstructured, but decided it would be best to specify TAU as we have done, for both scientific and ethical reasons. This is analogous to *D'Onofrio et al.*'s study of initiation of sublingual buprenorphine in the emergency department¹¹, where the design included a "facilitated referral" control condition that offered a structured brief intervention in addition to a straight referral (usual care) condition. TAU as specified provides a minimal standard of care that is clinically credible, and a comparison condition that is relatively consistent across sites.

4.0 Study Endpoints

Primary Outcome Measure--Retention in Medication Treatment for OUD: Enrollment in effective medication treatment for OUD (either buprenorphine maintenance, methadone maintenance, or extended-release naltrexone) will be ascertained through interview of the participant at each assessment point, using a modified, brief version of the Treatment Services Review¹² that records type and dose of medication treatment, contact information on the treatment program, and psychosocial treatment modalities accessed since the previous visit (e.g. professional counseling, 12-step group participation). At the key 12-week outcome point, we will ask for a release of information to contact the treatment program to verify medication type and enrollment. The primary outcome will be a binary indicator of whether or not the patient is enrolled on buprenorphine maintenance treatment or other effective medication (methadone maintenance or extended-release naltrexone) at 12 weeks after randomization, verified by either report from the treatment program, or if the treatment program does not respond, prescription drug monitoring report or EMR. Substantial evidence from longitudinal studies suggests that being on effective medication treatment for OUD is essential to maintaining abstinence, and risk of relapse to opioid use is high if buprenorphine or other medication treatment is discontinued.^{13,14} A binary indicator, while it sacrifices some information, has the virtue of having a straightforward clinical meaning, particularly in this trial where the goal is to determine whether the ID/LAB model, where the medical team directly manages OUD with LAB during hospitalization, increases the likelihood of transitioning successfully to medication maintenance treatment in the community. We will examine other measures of retention as secondary outcomes, such as total weeks engaged in medication treatment, pattern of retention in treatment across time, and participation in psychosocial treatment modalities. We considered as an alternative a primary outcome measure reflecting opioid use (e.g. opioid free weeks or abstinence as end of study often favored by the FDA, or opioid relapse as used in the in the X:BOT trial¹⁵ and in an XR-NTX vs. TAU CJS trial.¹⁶ However, the primary goal of the models of care being tested is to secure transition into long term-community based medication treatment for OUD. The opioid outcomes are likely to be strongly associated with continued MOUD treatment and will be key secondary outcomes.

We anticipate continuing enrollment and analyses concurrently for the first three years of the study. We will continue enrollment of new participants until month nine of year 4—to ensure that the great majority of participants have completed the six-month study and that all participants will be followed for a minimum of three months post-randomization.

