9.0 Consent Process

Participants will be provided with a study information sheet and will only be approached for a consent discussion if they express interest in learning more about the study. We expect most potential participants to be hospitalized, so consent will take place in a private setting in the hospital, such as their room. Patients who express interest in learning more about the study will have a consent discussion with the evaluating study physician, RA, or Nurse Coordinator. They will review the study with the potential participant, provide the consent form document for the potential participant to read, discuss the study answering any questions.

The Consent Form is long and detailed, and consists of a consent form and HIPAA authorizations. Our consent procedure is designed to ensure ample time to understand and discuss its content prior to completing the informed consent process. A Consent Summary is provided at the beginning of the consent form, and the research staff member consenting the participant will walk the patient through the summary and provide an overview of the consent form. The patient will then be given the time necessary to read the consent form and write down any questions. At least 20 minutes will be set-aside for this. The research staff member will then reconvene with the patient to review the Consent Form with the patient and address any questions or concerns.

Potential study participants who remain interested after review of the consent form will be given comprehension questions to ascertain their understanding of the study, including its purpose, procedures involved, and the voluntary nature of participation. For participants who do not correctly answer all comprehension items, research staff will re-explain the study, with a focus on aspects candidates did not understand. Participants may attempt the consent comprehension questions a maximum of three times before they are deemed unable to comprehend the study. Any participant who cannot demonstrate appropriate understanding of the study to research personnel will be ineligible to participate and will be assisted in finding other treatment resources if desired.

Study participants who demonstrate understanding of the study and who voluntarily agree to participate will be asked to sign the IRB-approved consent form that they reviewed and a copy of the signed consent will be given to the participant.

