- Adult ADHD Self Report Scale (ASRS) for ADHD symptoms³⁴ (4 mins) is an 18 question assessment for presence and severity of ADHD symptoms by self-report.

Quality of Life: WHOQOL-Bref³⁵ (5 mins) is a well validated and widely used scale for persons with substance use disorders that measures the quality of social and occupational functioning as well as other domains.

Medical/Infectious Disease Questionnaire: This form documents the completion of antimicrobial therapy and re-hospitalization for infection. The initial evaluation documents the relevant infection and medical details such as infection site, organism, and stage. It also extracts the type of anti-infective, route of administration, dose, planned duration and, at select sites, knowledge of, experience with, and attitudes related to HIV Pre-Exposure Prophylaxis (PrEP). Information collected on follow-up will be alteration of treatment plan, infection related adverse events (e.g. PICC complications, drug reaction/toxicity to anti-infective agent prescribed by non-study clinicians, etc), intervening hospitalizations, and questions related to PrEP. Current study participants, at select sites, who are beyond the hospital-discharge timepoint will be asked these PrEP questions retrospectively, at one timepoint, at the next scheduled study follow-up visit.

Severity Scoring: The Elixhauser Comorbidity Index³⁶ is a validated scoring index for predicting mortality based on patient comorbidity. This will be performed via chart review.

Substance Use Treatment (SUTx) Form: This questionnaire documents the details of MOUD and substance use treatment history in the intervention and TAU arms. For those participants receiving LAB, it documents date of administration, dose, location and prescribing provider. The TAU section of the questionnaire queries the variety of different forms a substance use treatment that participants may or may not receive in the community. This includes MOUD (buprenorphine, extended-release naltrexone, or methadone) prescribed by non-study related physicians, behavioral therapy (i.e. 12 step

programs), and whether participants have enrolled in a community opioid treatment program (OTP).

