(WHOQOL-Bref); continuous); 2) Opioid craving (continuous); 3) Pain (Modified PEG scores; continuous).

Intent to Treat, Dropouts, and Missing Data: All analyses will be on the Intent-to-treat (ITT) sample, i.e., all randomized subjects (N=200) according to the treatment arm to which they were assigned. For the primary outcome and secondary outcomes related to treatment engagement, any patients lost to follow-up will be assumed not to be enrolled in treatment nor to have completed the antimicrobial course. Loss to follow-up will be minimized through collection of extensive locator information at baseline and proactive outreach, as described above. For the secondary outcomes related to substance use, missing data (patients who cannot be located) will be assumed to be opioid positive (not abstinent), a typical assumption which is reasonable based on the high rate of relapse among patients with OUD who discontinue medication treatment.^{14,44-46} For other secondary outcomes, missing data will be treated as missing at random. Longitudinal mixed effects models do not require complete data to provide estimates of the outcome, and the estimates are considered valid under the assumption that the data are missing at random.⁴⁷ We will additionally perform sensitivity analysis for the secondary outcomes to examine the influence on the outcomes of dropout and missing data by performing several imputation methods, for instance imputing missing weeks as all abstinent or all non-abstinent. Comparison of the inferences from assuming various models for the missingness provides a measure of the validity of the efficacy estimate from the initial model.

Significance Testing and Preliminary Analyses: All tests for main effects will be performed at two-sided significance level of 5%. Before performing specific analyses, we will examine the distributions of outcome measures and covariates and investigate for outliers. The distributions of continuous variables will be checked for normality, and transformed, if necessary. Distribution of demographic and other baseline variables will be examined and described in terms of means, standard deviations, proportions and 95% confidence intervals. Covariates will be examined for association with treatment outcome. Covariates associated with treatment outcome will be adjusted for in models used to test study hypotheses.

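### The release needed to ask a treatment program about the primary outcome is scheduled only at week 12, so treated patients in either arm who are not reached then can be scored as not enrolled

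*Combined protocol and SAP*

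**What the plan says.** Section 4.0 (Primary Outcome Measure) has participants interviewed about treatment at each assessment point. The interview form records, among other things, "contact information on the treatment program". The permission to use those details comes later: "At the key 12-week outcome point, we will ask for a release of information to contact the treatment program". Verification is by program report, "or if the treatment program does not respond, prescription drug monitoring report or EMR".

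No other section of the available text schedules a release. Section 9.0 says that the consent document "consists of a consent form and HIPAA authorizations", without saying whether any authorization reaches an outside treatment program.

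Section 12.0 (Intent to Treat, Dropouts, and Missing Data) closes the sequence for the primary outcome: "any patients lost to follow-up will be assumed not to be enrolled in treatment nor to have completed the antimicrobial course". It states no exception for a patient whose treatment a program or a record could confirm.

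**The concern.** The plan's preferred source depends on a permission that it asks for at the moment when contact may already have been lost. Take a participant who names a clinic at week 4, stays on medication there, and cannot be found at week 12. The study holds the clinic's details but, on the written plan, no permission to call. The written trigger for the back-up records is a program that does not respond. It does not mention a program that was never asked, or a release that was refused. The participant then counts as a failure.

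This affects the primary endpoint. Every treated patient scored as untreated lowers the observed rate in that arm, and the loss could be avoided by moving one form to an earlier visit.

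**Working it through.** **Inputs from section 12.0 (Power Analysis):** 100 per arm, two-sided 5%, 40% on TAU, 59.7% on ID/LAB, 80% power. **Not in the documents:** the proportion not reached at week 12, how many of them are on treatment, and how many other records would find. These are assumed below.

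**Step 1: reproduce the plan's figure.** Use the normal approximation with pooled variance under the null and no continuity correction.
- Pooled rate = (0.40 + 0.597)/2 = 0.4985; SE0 = √(2 × 0.4985 × 0.5015/100) = 0.0707.
- SE1 = √((0.40 × 0.60 + 0.597 × 0.403)/100) = 0.0693.
- Power = Φ((0.197 − 1.96 × 0.0707)/0.0693) = Φ(0.84) = 0.800, as stated.
- Odds ratio = (0.597/0.403)/(0.40/0.60) = 2.22, as stated.

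**Step 2: loss from unverifiable treated patients, same process in both arms.** Let m be the share missed, r their treatment rate relative to their arm's overall rate, and c the share of treated missed patients confirmed by some other record. The observed rate is p × (1 − k), with k = m × r × (1 − c). Put the reduced rates into the Step 1 formula:

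| k | TAU | ID/LAB | Difference (points) | Power |
|---|---|---|---|---|
| 0 | 40.0% | 59.7% | 19.7 | 0.800 |
| 0.05 | 38.0% | 56.7% | 18.7 | 0.759 |
| 0.10 | 36.0% | 53.7% | 17.7 | 0.716 |
| 0.20 | 32.0% | 47.8% | 15.8 | 0.626 |
| 0.30 | 28.0% | 41.8% | 13.8 | 0.535 |

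With r = 1 and c = 0, k equals the share missed, so 10% missed gives 0.716 and 20% gives 0.626. That is the worst case for a given m when r does not exceed 1. If missed patients are treated at half their arm's rate, or if half of the treated ones are found in other records, k halves: 10% missed then gives 0.759 and 20% gives 0.716.

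In this symmetric case a true effect is diluted, but equal true rates stay equal and the type I error stays at 5%.

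**Step 3: what it would take to bias the comparison.** Suppose both true rates are 50%, 20% are missed in each arm, and a share s of treated missed ID/LAB patients is confirmed from the study's own injection records, with no counterpart in TAU. TAU is observed at 0.50 × 0.80 = 40% and ID/LAB at 0.50 × (0.80 + 0.20s).
- s = 0: difference 0 points, rejection rate 5%.
- s = 25%: 42.5% against 40%, 2.5 points, rejection rate 6.5%.
- s = 50%: 45% against 40%, 5 points, rejection rate 11%.

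No passage gives a value for s.

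**The case against.** **Only at week 12 is an inference.** It rests on finding no other release step. The authorizations signed at enrolment are not in the text reviewed and may already cover outside programs. This stands as a condition on the point.

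**Few patients may be affected.** Section 10.0 allows assessments in the field or by telephone, section 14.0 provides for community tracking, and a late request at week 24 is not excluded. This narrows the group to people not reached at all around week 12. It does not empty it: section 14.0 itself foresees lost contact and refusal.

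**The back-up could be read more widely.** A program that cannot be asked also gives no response, so prescription-monitoring and EMR checks might be applied. That is a fair reading, but the text should state it, and section 12.0 still scores a lost patient as not enrolled.

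**The design rates may already absorb the loss.** If 40% and 59.7% were meant as verified rates with lost patients counted as failures, planned power does not fall; the fix would instead raise the rates observed. The plan does not say which is meant.

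**A stronger reading is tempting: that the gap favours ID/LAB.** Study injections are documented on the study's own form ("For those participants receiving LAB, it documents date of administration, dose, location and prescribing provider") and need no release, whereas medication in TAU comes from outside. Assuming that 25–30% of TAU and 15% of ID/LAB are missed, that 20–40% of them are treated, and that 0–50% of those are found elsewhere, the spurious difference runs from 0.10 × 0.20 × 0.5 = 1 point to 0.15 × 0.40 × 1 = 6 points. With equal true rates of 50%, 3 points gives a rejection rate of 7.1% and 6 points gives 13.6%. All of this comes from the assumed gap in miss rates, which no passage supports; reversing that gap reverses the sign. The documents also point the other way. Section 10.0 gives TAU nurse contact on a schedule like that of ID/LAB. ID/LAB care is "followed by referral as soon as possible after hospital discharge to community resources for long term treatment of OUD", so its successfully transferred patients depend on outside reports too. The study schedule shows injections at baseline, week 4 and week 8, and nothing says whether a week-8 dose counts as enrolment at week 12.

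**Conclusion.** The point holds as a procedural weakness in how the primary outcome is verified. The plan collects program details early and, on the available text, seeks permission to use them late. Its written back-up trigger and scoring rule do not rescue a treated patient who is not reached at week 12. Patients of either arm in outside care are exposed.

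The consequence that can be shown is lower observed rates and lower power: about 0.72 at 10% missed and 0.63 at 20%. This rests on assumed miss rates, treatment among missed patients at their arm's rate, no confirmation from any source, and the design rates being true enrolment rates. Relaxing the second or third assumption shrinks the loss toward zero.

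Differential verification is possible, but the documents do not support a claim that the trial is biased toward ID/LAB or an inflated false-positive rate of any particular size. The stated sample size and power calculation are not in dispute.

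**What to change.** 1. Ask for the release at enrolment, alongside the authorizations in section 9.0, and confirm or extend it at each visit where a program is named. The renewal matters because the documents do not show that programs would accept a release signed before they were named. If the existing authorizations already cover outside programs, say so in section 4.0.
2. At week 12, use the release to contact the last-named program for participants who are not reached.
3. Search prescription-monitoring and EMR records for every participant without a program report, whether the reason is no contact, no release, refusal or non-response, and do so identically in both arms.
4. Amend the missing-data rule in section 12.0 so that not enrolled is assigned only when none of these sources confirms treatment. Without this, an earlier release need not change any score.

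The cost is one extra form, a short amendment, some refusals or revocations, and a modest number of extra program and record checks. No visit is added, and the sample size and the primary model are unchanged.
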